- To determine toxicity, polyneuropathy in specific, during induction treatment and maintenance treatment with ixazomib citrate or placebo
- ♦ To determine progression free survival and overall survival from registration
- ♦ To compare the efficacy between maintenance treatment with ixazomib citrate versus placebo determined as overall survival from randomization
- To determine the efficacy of maintenance therapy determined as an improvement in response during maintenance treatment with ixazomib citrate or placebo
- ♦ To determine efficacy of induction therapy determined as time to response
- ♦ To determine feasibility, defined as discontinuation rate due to toxicity, during induction treatment and maintenance treatment with ixazomib citrate or placebo
- To determine time to next treatment
- To determine PFS on second line therapy
- To determine Quality of Life during induction treatment and maintenance therapy with Ixazomib or placebo
- To identify clinical, imaging-related and molecular markers prognostic and predictive for outcome and toxicity
- To establish second primary malignancies (SPM)

7 Study design

This is a multicenter phase II clinical trial, with upfront registration and late double-blind, placebocontrolled, maintenance randomization. Details of all treatments (dose and schedule) are given in section 9 and appendix F, G and H.

- 1. Patients will be registered, and then they will be treated with 9 cycles of induction therapy* with ixazomib citrate— thalidomide low dose dexamethasone;
- 2. After induction, patients eligible for randomization will be randomized double-blind between maintenance treatment with ixazomib citrate versus placebo.

The primary objective of this trial is to assess whether maintenance with ixazomib citrate improves PFS (calculated from date of randomization) as compared to placebo. This is used for the sample size calculation. This trial is therefore a superiority trial.

* Randomization and subsequent start of maintenance therapy is allowed after a minimum of 6 induction cycles as described in 8.2.1.

8 Study population

All eligible patients have to be registered before start of treatment. After the induction treatment patients will be randomized.

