9.1 Induction treatment with ixazomib citrate/thalidomide/low dose dexamethasone

9.1.1 Treatment schedule

Induction therapy should start within 4 weeks after patient registration. Patients will receive 9 cycles of ixazomib citrate (4 mg) on days 1, 8, 15 of a 28-day cycle and a daily dose of thalidomide (100 mg) continuously plus dexamethasone (40 mg) on days 1, 8, 15 and 22.

Agent	Dose/day	Route of administration	Days
Ixazomib citrate	4 mg	p.o	1,8 and 15
Thalidomide	100 mg	p.o	1 - 28
Dexamethasone	40 mg	p.o.	1, 8, 15 and 22

After cycle 1, 3, 5, 7 and 9 evaluation will take place. In case of progressive disease after cycle 3, 5, 7 or 9 patients will go off protocol treatment.

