The grading of adverse events will be done using the NCI Common Terminology Criteria for Adverse Events, CTCAE version 4.0. A complete document may be downloaded from the HOVON website:

http://www.hovon.nl (under Trials > General information about studies)

F. Intake of ixazomib citrate and management of ixazomib citrate toxicity during an induction cycle and maintenance therapy

Ixazomib citrate will be given as a single, oral dose of 4.0 mg weekly (Days 1, 8, and 15) for 3 weeks, followed by 1 week without study drug in a 28-day cycle. Patients should be instructed to swallow ixazomib citrate/placebo capsules whole with water and not to break, chew, or open the capsules. Ixazomib citrate should be taken on an empty stomach, at least 1 hour before or no sooner than 2 hours after a meal. The capsule should be swallowed with a sip of water. A total of approximately 150 mL of water should be taken with the capsules. Missed doses can be taken as soon as the patient remembers as long as the next scheduled dose is 72 hours or more away. A double dose should not be taken to make up for a missed dose. If the patient vomits after taking a dose, the patient should not repeat the dose but should resume dosing at the time of the next scheduled dose.

[figure not shown]
Dose levels

Dose Levels for ixazomib citrate during Induction and Maintenance Therapy

Dose Levels	Ixazomib citrate
Starting Dose	4 mg once weekly on days 1,8 and 15 every 28 days
Dose Level -1	3 mg once weekly on days 1,8 and 15 every 28 days
Dose Level -2	2,3 mg once weekly on days 1,8 and 15 every 28 days
Dose Level -3	discontinue (off protocol treatment)

Dosage adjustments for hematologic toxicity.

See flow sheet and table at next pages.

Dose adjustments for hematological toxicities

Criteria	Action
Within-Cycle Dose Modifications - If platelet count ≤ 30 × 109/L or ANC ≤ 0.50 × 109/L on a MLN9708 dosing day (other than Day 1)	 MLN9708 dose should be withheld. Complete blood count (CBC) with differential should be repeated within one week or earlier at the discretion of the physician until the ANC ≥ 1.0x10⁹/L and/or platelet counts ≥ 75x10⁹/L. Upon recovery within the cycle, MLN9708 may be reinitiated with 1 dose level reduction.

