≥ Grade 2	Maintain dose level when dosing restarted at next cycle at discretion of treating	
	physician.	

Thalidomide is not reduced for for hematologic toxicity

H. Intake of dexamethasone and management of dexamethasone related toxicity

Dexamethasone will be given as a single, oral dose of 40 mg/day weekly on Days 1, 8, 15, and 22 of a 28-day cycle. Dexamethasone should be taken at approximately the same time each day. Dexamethasone should be taken at least 1 hour after ixazomib citrate and thalidomide. Each dose of dexamethasone should be taken with food or milk. If a dose of dexamethasone is missed, the dose should be taken as soon as the patient remembers it. If it is almost time for the next dose (within 6 hours), the missed dose should be skipped and the next dose taken according to the regular dosing schedule. A double dose should not be taken to make up for a missed dose. If the patient vomits after taking a dose, the patient should not repeat the dose but should resume dosing at the time of the next scheduled dose.

Dose Levels for Dexamethasone during Induction Therapy

Dose Level	Prednisone
Starting Dose	40 mg once weekly on days 1,8 and 15 every 28 days
Dose Level -1	20 mg once weekly on days 1,8 and 15 every 28 days
Dose Level -2	8 mg once weekly on days 1,8 and 15 every 28 days
Dose Level -3	discontinue

Dose Modification Instructions for Dexamethasone during a Cycle

Toxicity	Prednisone Dose Modification
Dyspepsia = Grade 1-2	Maintain dose and treat with histamine (H2) blockers or proton pump inhibitors. Decrease by one dose level if symptoms persist.
Dyspepsia ≥ Grade 3	Hold dose until symptoms are controlled. Add H2 blocker or proton pump inhibitors and decrease one dose level when dose restarted.
Edema ≥ Grade 3	Use diuretics as needed and decrease dose by one dose level.
Confusion or mood alteration ≥ Grade 2	Hold dose until symptoms resolve. When dose restarted decrease dose by one dose level.
Muscle weakness (steroid myopathy) > Grade 2 Interfering with function	Decrease by one dose level. If weakness persist despite these measures, decrease dose by one dose level. Discontinue dexamethasone and do not resume if symptoms persist
Hyperglycaemia ≥ Grade 3	Treat with insulin or oral hypoglycaemic agents as needed. If uncontrolled despite these measures decrease dose by one dose level until levels are satisfactory
Acute pancreatitis	Discontinue dexamethasone and discontinue subject from the study.

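### Appendix H gives dexamethasone on three days per cycle in its dose-level table but on four days in its own text and in section 9.1.1, and does not say whether day 22 survives a dose reduction

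*Protocol*

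**What the plan says.** Section 9.1.1 sets out nine 28-day induction cycles, with ixazomib and thalidomide "plus dexamethasone (40 mg) on days 1, 8, 15 and 22". The table under that text lists the same four dexamethasone days. Appendix H opens in agreement: "Dexamethasone will be given as a single, oral dose of 40 mg/day weekly on Days 1, 8, 15, and 22 of a 28-day cycle".

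The dose-level table that follows in Appendix H is titled for dexamethasone but gives three days at every active level:

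- starting dose: "40 mg once weekly on days 1,8 and 15 every 28 days"
- level -1: "20 mg once weekly on days 1,8 and 15 every 28 days"
- level -2: "8 mg once weekly on days 1,8 and 15 every 28 days"

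Level -3 is discontinuation. The dose column of this table is headed Prednisone, and so is the action column of the dose-modification table below it, although both tables have dexamethasone in their titles.

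On where the schedule is to be found, section 7 says: "Details of all treatments (dose and schedule) are given in section 9 and appendix F, G and H". Section 9.1.2 sends the reader to Appendix H for taking and reducing dexamethasone. Neither place says which text prevails if they differ.

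**The concern.** These are operative dosing instructions for one of the three induction drugs, and they conflict within a single appendix. At the starting dose a reader can find support for either three or four doses per cycle. At the reduced levels the position is less clear still, because section 9.1.1 and the Appendix H text speak only of 40 mg. The table alone gives days for 20 mg and 8 mg. One site could keep day 22 after a reduction and another drop it, and both could point to the protocol.

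At stake is whether all registered patients are offered the same induction regimen. Response after induction is listed in section 13.1 as a primary endpoint, and section 6 lists induction toxicity and discontinuation for toxicity among the secondary objectives. All of these describe a regimen that should have one planned schedule. Without one, an omitted day-22 dose cannot be classed unambiguously as planned, reduced or missed.

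**Working it through.** **Inputs.** Doses of 40, 20 and 8 mg (Appendix H dose-level table); four dosing days (section 9.1.1 and Appendix H text) or three (Appendix H table); nine cycles (section 9.1.1), with randomization possible after six in defined circumstances (section 8.2.1).

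**Step 1: the places side by side (starting dose).**

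| Place | Days in a 28-day cycle |
|---|---|
| Section 9.1.1, text | 1, 8, 15, 22 |
| Section 9.1.1, table | 1, 8, 15, 22 |
| Appendix H, opening text | 1, 8, 15, 22 |
| Appendix H, dose-level table | 1, 8, 15 |

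For levels -1 and -2 only the last row has an entry.

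**Step 2: planned exposure per cycle** = mg per dose × dosing days.

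| Level | Four days | Three days | Shortfall |
|---|---|---|---|
| Starting | 4 × 40 = 160 mg | 3 × 40 = 120 mg | 40/160 = 25% |
| -1 | 4 × 20 = 80 mg | 3 × 20 = 60 mg | 20/80 = 25% |
| -2 | 4 × 8 = 32 mg | 3 × 8 = 24 mg | 8/32 = 25% |

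Over nine unreduced cycles the starting level gives 9 × 160 = 1440 mg or 9 × 120 = 1080 mg, a difference of 360 mg. Over six cycles it is 960 or 720 mg. The proportion is 25% whatever the number of cycles.

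**Step 3: size of a one-level reduction.**

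- Four days throughout: 160 to 80 mg per cycle, a 50% cut.
- Three days throughout: 120 to 60 mg, also 50%.
- Four days at the start and the table after reduction: 160 to 60 mg, which is 100/160 = 62.5%.

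The two consistent readings agree on the proportional step. Only the mixed reading makes it larger.

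**Step 4: does this touch the planning figures?** Section 14.1 gives a standard error of about 3% for an assumed 80% response rate in 142 patients. √(0.8 × 0.2 / 142) = 0.0336, so the figure reproduces. The Freedman calculation at HR 0.39, 90% power and two-sided 5% gives 55 events, as stated. Dexamethasone days enter neither calculation.

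**The case against.** The strongest reply is that the table is a copying slip. Three of the four places give four days at the starting dose. The three-day wording matches the ixazomib row in Appendix F, "4 mg once weekly on days 1,8 and 15 every 28 days", and the Prednisone headings also look like carried-over text. This is plausible for the starting dose, and it is why the regimen as a whole should not be called undefined. It does not settle the reduced levels, where the table stands alone, and the protocol itself offers no rule for choosing.

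Several stronger readings are tempting but not supported:

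- **A biased response rate or PFS comparison.** The difference can be sized only in milligrams; the protocol has nothing that converts it into response. Induction is common to all patients and precedes randomization, so the PFS comparison is not directly affected. Section 14.2.4 also treats everything except the analysis behind the sample size as hypothesis-generating.
- **Sites taking the starting dose from the table.** Section 9.1.2 refers to Appendix H for intake and reduction, while section 9.1.1 sets the starting regimen.
- **Damage to a dose-intensity analysis.** No such endpoint or analysis is planned; feasibility is measured by discontinuation for toxicity.
- **Actual use of the wrong drug.** The table titles and several entries name dexamethasone. The headings are an error to correct, but confusion between drugs is not shown.
- **A demonstrated safety harm.** At the starting dose the table gives less than section 9.1.1, and the documents identify no resulting harm.

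**Conclusion.** The contradiction is literal, stands in current text and cannot be resolved from the protocol. It is an internal inconsistency in a dosing instruction, not a flaw in the statistical design.

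Its size is 25% of planned dexamethasone per cycle at each dose level, with a one-level reduction of 50% under either consistent reading and 62.5% under the mixed one. These figures assume full delivery of the scheduled doses at a given level. They describe what the plan prescribes and say nothing about what was given.

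The practically open question is whether day 22 continues at levels -1 and -2. The consequence is limited to the consistent definition and delivery of the induction regimen whose response rate and toxicity will be reported. The number to randomize, the 55 events, the precision of the response rate and the randomized comparison all stand.

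**What to change.** The sponsor should bring section 9.1.1, the opening text of Appendix H and the Appendix H dose-level table to one set of dexamethasone dosing days, stated explicitly for the starting dose and for levels -1 and -2. The clinical team decides which schedule applies; this review takes no position. The Prednisone headings in both Appendix H tables should be changed to the drug that the tables concern, and sites should be told of the correction.

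The cost is a corrected appendix page, an edit to section 9.1.1 if needed, and a letter to sites. No change to the CRF is required: section 16.1 already provides for recording when and how much protocol treatment was given, so the schedule actually followed can be described for patients already treated. Design, sample size and analysis stay as they are.

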	9.1 Inclusion criteria	
10	REQUIRED CLINICAL EVALUATIONS	102
	10.1 Required investigations apart from the HOVON126/NMSG21.13 pr	rotocol102
11	ENDPOINTS	103
	11.1 Primary endpoint	103 103
12	DATA COLLECTION	103
13	STATISTICAL CONSIDERATION	104
14	REFERENCES	106
V	DOSITION EMISSION TOMOGRAPHY METHODS	100

3 Synopsis

Study phase

Prospective systematic evaluation

Study objectives

Primary objectives:

- To assess the prognostic value of FDG-PET at diagnosis in terms of progression free survival (PFS).

- To determine the conversion rate, defined as complete normalization, of FDG-PET after induction therapy

Secondary objectives:

- To compare the response rate as determined by FDG-PET with classical biochemical response monitoring according to IMWG
- To assess the prognostic value of FDG-PET-CT at diagnosis in terms of overall survival (OS)
- To assess the prognostic value of post-induction remission status as determined with FDG-PET in terms of PFS and OS
- To compare the prognostic value of post-induction remission status as determined with FDG-PET with the minimal residual disease (MRD) status
- To correlate MM related bone disease as detected by FDG-PET-CT with distinct patterns of gene expression of malignant plasma cells and of the bone marrow microenvironment

Study design Side study of HOVON126/NMSG21.13

Patient population Patients included in HOVON126/NMSG21.13

Number of patients 60

Planned start and end of Running time HOVON126/NMSG21.13

recuitment Start Q2 2015

End Q4 2016

4 Investigators and study administrative structure

Responsibility	Name	Affiliation/Address
Principal Investigator	[name]	VU University Medical Center Amsterdam
Executive coordinator	[name]	VU University Medical Center Amsterdam
Study Coordinators	[name]	Erasmus MC Cancer Institute Rotterdam
	[name]	VU University Medical Center Amsterdam
	[name]	University Hospital Trondheim
Representative of	[name], chairman	VU University Medical Center Amsterdam
Sponsor (HOVON)	[name]	[name]
Registration	[name]	[contact] VU University Medical Center Amsterdam
Monitoring		vo oniversity inedical center Amsterdam
- Clinical data	HOVON Data Center	Erasmus MC Cancer Institute – Clinical Trial Office
- Imaging	Imaging Center	VU University Medical Center Amsterdam
Writing Committee	[name]	Odense University Hospital Odense
	[name]	Erasmus MC Cancer Institute Rotterdam
	[name]	Erasmus MC Cancer Institute Rotterdam

5.1 Introduction

Bone disease, defined as osteolytic lesions and osteoporosis, is common in patients with symptomatic/stage III Multiple Myeloma (MM), with up to 90% of patients developing bone lesions and up to 60% of patients experiencing a pathologic fracture in the course of the disease. The hallmark of myeloma bone disease is a disbalance between bone resorption and deposition of new bone through increased osteoclast activity and inhibition of osteoblasts by Dickkopf-1 and frizzle-related protein 2 produced by MM cells, respectively.² The clinical consequences of imbalanced bone destruction include bone pain, pathologic fractures, hypercalcemia and spinal cord compression syndromes, which can be devastating for patients and significantly impact overall quality of life. Moreover, the presence of lytic bone disease has been found to be of prognostic importance, reflected by the Salmon and Durie clinical staging system.³ Patients without or with one lesion only, defined as stage I, showed an overall survival (OS) of approximately 7 years as compared to 2-3 years in patients with stage III, which can be diagnosed in case of more than 1 osteolytic lesions. More recently, the presence of only one osteolytic lesions on whole body X-ray (WBXR) was found to be an independent prognostic factor. 4 Although, the prognostic value of osteolytic lesions detected by CT is not supported by prospective data the International Myeloma Working Group (IMWG) recently decided that an osteolytic lesion of more than 5 mm definitely indicates the presence of MM bone disease. Therefore, in the guidelines of the International Myeloma Working Group (IMWG), apart from other criteria, the presence of one or more bone lesions either on WBXR or CT-scan indicates the presence of symptomatic MM, for which treatment is required.⁵ Because of the devastating effects of bone disease and the fact that the sensitivity of conventional WBXR analysis is low, given that at least 30% of trabecular bone substance must be lost in order to give rise to visible lytic lesions in many centres a CT-scan of the whole body is now being performed in order to detect MM related bone disease. CT has been found to have a superior detection rate as compared to WBXR, although lesions in the skull, the ribs and extremities might be missed. 16

5.2 Prognostic impact of bone disease detected by FDG-PET at diagnosis of MM

As indicated, in contrast to its high sensitivity for the detection of bone disease, whole body CT was not found to be of prognostic value for the clinical outcome. In contrast, recently, data on the prognostic value of baseline FDG-PET-CT were published by two groups. The extent of the disease, defined as the number of FDG-positive lesions as well as the maximum Standard Uptake Value (SUV) at diagnosis was found to be correlated with inferior outcome. In the 'Total Therapy 3'-study, Bartel et al. found that the presence of more than three focal lesions, as well as the presence

of extramedullary disease (EMD) at baseline was correlated with poor outcome: 5-year OS was 73% versus 90% and 50% versus 87%, respectively. Recently, Zamagni et al. had similar findings by showing a correlation between the presence of extramedullary disease (EMD) or high SUV and outcome (EMD: 4-year OS 64% versus 90%; SUV >4,2: 76% versus 92%).{Zamagni, 2011}

5.3 Quality of response by using FDG-PET in relation to prognosis

The international myeloma working group has defined international uniform response criteria. New treatment options, leading to a high complete remission (CR) rate, recently led to the introduction of molecular CR determined by allele-specific oligonucleotide polymerase chain reaction (ASO-PCR) of rearranged B-cell receptor genes and immunophenotypic CR determined by multiparametric flowcytometry (MFC) as response criteria, both indicating a deeper level of response. ⁹⁻¹³ Although accomplishing molecular or immunophenotypic CR is a predictor of superior outcome, still such patients do develop relapses. Besides an insufficient sensitivity of techniques used to detect minimal residual disease (MRD), the presence of focal disease can explain why relapses occur even in MRD-negative patients. The studies investigating the prognostic value of FDG-PET scans support this hypothesis. Reaching FDG-PET negativity (PET-CR or complete metabolic response (CMR)) during the course of the treatment resulted in an improved outcome. The 30-month estimated EFS was 89% in PET-CR versus 63% for those with persistent FDG uptake in the study of Bartel. ⁷ These numbers were 92% and 71% for OS. Similarly, in the study of Zamagni et al. {Zamagni, 2011} PFS and OS were superior in case of PET-CR versus those without PET-CR; the 4-year estimates of PFS and OS were 47% and 79% respectively versus 32% and 66% in PET-positive patients.

5.4 Biological features of MM related bone disease; Do specific gene expression profiles of malignant plasma cells or the plasma cell negative bone marrow fraction predict MM bone disease?

GEP of malignant plasma cells allow to define the molecular classification of MM, revealing 7 distinct molecular entities. Among these a gene profile associated with less bone disease (GEP LB) was associated with superior survival.¹⁹ Further analysis showed a high expression of the IL-6 ligand receptor and low expression of Wnt signalling antagonists FRZB and DKK-1.²⁰ Bartel et al. found a similar inverse correlation between GEP-LB and the number of focal lesions at FDG-PET.

Conversely, a high risk GEP was found in the group of patients with bone disease detected by FDG-PET, MRI and WBXR.⁷ Recently, in the Dutch-Belgian/German HOVON-65/GMMG-HD4 trial hierarchical clustering identified 10 subgroups; 6 corresponded to clusters described in the University of Arkansas for Medical Science (UAMS) classification, CD-1 (n = 13, 4.1%), CD-2 (n = 34, 1.6%), MF

(n = 32, 1.0%), MS (n = 33, 1.3%), proliferation-associated genes (n = 15, 4.7%), and hyperdiploid (n = 32, 1.0%)= 77, 24.1%). Moreover, the UAMS low percentage of bone disease cluster was identified as a subcluster of the MF cluster (n = 15, 4.7%). One subgroup (n = 39, 12.2%) showed a myeloid signature. Three novel subgroups were defined, including a subgroup of 37 patients (11.6%) characterized by high expression of genes involved in the nuclear factor kappa light-chain-enhancer of activated B cells pathway, which include TNFAIP3 and CD40. Another subgroup of 22 patients (6.9%) was characterized by distinct overexpression of cancer testis antigens without overexpression of proliferation genes. The third novel cluster of 9 patients (2.8%) showed up-regulation of protein tyrosine phosphatases PRL-3 and PTPRZ1 as well as SOCS3. There is limited information on the GEP of the plasma cell negative bone marrow fraction. Several groups have reported that BM-derived mesenchymal stem cells from MM patients (MM-hMSCs) show a distinctive gene expression profile and an enhanced production of cytokines, including IL-6, DKK1, IL-1ß, and SDF-1 as compared to normal donor-derived hMSCs (ND-hMSCs). 21;22 In addition, impaired osteogenic differentiation ability, compared to ND-hMSCs has been found.²³ However, these are cultured hMSCs. Firstly, this is laborious and secondly, by culturing, GEP might have been altered. Although GEP of the negative bone marrow fraction following CD138 isolation is hampered by being a heterogeneous cell population, we plan to perform GEP not only of malignant plasma cells but also from the remaining non-plasma cell containing bone marrow fraction, in order to investigate whether specific gene profiles are related to bone disease as defined by FDG-PET-CT.

